**APPENDIX – 1**  
**LIST OF ABBREVIATIONS**

AAN	American Academy of Neurology
CIDP	Chronic Inflammatory Demyelinating Polyneuropathy
CIP-PRO20	Chronic Immune-mediated Polyneuropathy – Patient Reported Outcome Scale
HHD	Hand-held Dynamometry
INCAT	Inflammatory Neuropathy Cause and Treatment
IVIG	Intravenous Immunoglobulins
PLEX	Plasma Exchange
QOL	Quality of Life
R-ODS	Rasch-built Overall Disability Scale
SC	Subcutaneous
SCIG	Subcutaneous Immunoglobulins
SE	Side Effects
SF-36	Medical Outcome Study 36-item Short Form Health Status Scale
TSQM	Treatment Satisfaction Questionnaire for Medication
USF	University of South Florida
USF CRC	USF Clinical Research Center

**APPENDIX – 2**  
**RELAPSE RESCUE PROTOCOL**

## APPENDIX – 3

## CIP-PRO20 Scale 2014

Protocol: A Study of Subcutaneous Immunoglobulin as Chronic Treatment for Patients with Chronic Inflammatory Demyelinating Polyneuropathy				CIP-PRO
Are you able to:	0: Not at all	1: A little bit	2. A lot	
I am frustrated by my neuropathy.				
I am bothered by pain from neuropathy.				
I am off balance when walking because of my neuropathy.				
I have trouble getting dressed because of my neuropathy.				
I have trouble sleeping because of my neuropathy.				
I am bothered by limitations in performing my work (include work at home) because of my neuropathy.				
I have trouble driving because of my neuropathy.				
I am dependent on others because of my neuropathy.				
I am depressed about my neuropathy.				
I am falling because of my neuropathy.				
I am preoccupied with my neuropathy.				
I am unable to do all the leisure activities that I want to do because of my neuropathy.				
I am worn out because of my neuropathy.				
I have trouble eating because of my neuropathy.				
I have trouble doing activities around the house.				
				Total Score: _____
Completed by: _____				Date: _____

## APPENDIX 4

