**Exclusion Criteria:**

- 1) Thrombocytopenia or other bleeding disorders;
- 2) Patients on anticoagulation therapy with an INR > 3.5;
- 3) Severe or anaphylactoid reactions to IVIG;
- 4) Cancer (active or currently treated);
- 5) Pregnancy;
- 6) Breast-feeding;
- 7) Renal insufficiency (creatinine > 1.5 upper limit of normal) or failure;
- 8) Congestive heart failure;
- 9) Psychiatric illness that would interfere with ability to provide informed consent or adhere to protocol;
- 10) Current IVIG doses greater than 2 g/kg per month;
- 11) Subject with an IgA level < 5% lower limit of normal;
- 12) History of active infection with HIV, Hepatitis B or Hepatitis C;
- 13) Presence of any other medical condition, which in the opinion of the investigator might interfere with performance;
- 14) Participation in a trial of an investigational medicinal product for CIDP in the past 12 weeks.

**Sample size and statistical analysis:** Descriptive information for the rate of change, such as mean and standard deviation, will be calculated. Due to the small sample size and self-control used in this study, instead of using paired t-test, Wilcoxon paired ranked test will be used to compare the change of before and after from each patient. Significance level is defined as 0.05 and all of the analyses will be carried by SAS (version 9.2).

**DESIGN:** The study will be submitted to the USF IRB for approval.

**Specific Aim #1.** We will assess QOL using the Medical Outcome Study 36-item short form health status scale (SF-36) and the Rasch-built Overall Disability Scale (R-ODS). The scales have been validated in patients with CIDP (Merkies et al, 2002; van Nes et al, 2011). We will also do a survey of side effects and satisfaction with treatment (using the Treatment Satisfaction Questionnaire for Medication, or TSQM) and CIP-PRO20 scale (used by permission from [name]; see appendix 3). No surveys will be completed until the patient signs the ICF. In addition, we will determine whether patients currently treated with IVIG would be willing to try the SC route of administration. Reasons cited for unwillingness to switch will be collected.

Specific Aim #2. To test the safety and tolerability of SCIG and feasibility of self-administration in patients with CIDP.

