1. CBC with differential count and platelet count will be done prior to treatment and once per month during treatment.
2. Symptom monitoring will be done via phone and at scheduled visits at regular intervals. Study visits will have a window of +/- 7 days. Patients will have 24/7 access to investigators to report any symptoms that develop.
3. Subjects will be provided with emergency contact number for questions relating to any symptoms during the study.
4. In the event that the subject experiences a reaction at home, they will call us. They will also be trained to call 911 in an emergency situation.

Primary End-Points.

1. Significant side-effects requiring withdrawal from study.
2. Laboratory abnormalities requiring discontinuation of study.

**Table 2.** Schedule of Study Events and Visits.

	Screening	Day 1	Week 1	Week 2*	Week 3*	Week 4 (Month 1)	Week 8 (Month 2)	Week 12 (Month 3)	Week 16 (Month 4)	Week 20 (Month 5)	Week 24 EOS/ET (Month 6)	Follow-Up
	V1	V2	V3	V4	V5	V6	V7	V8	V9	V10	V11	V12
Informed Consent	x											
Inclusion/Exclusion Review	x	x										
Medical History	x	x	x									
Vital Signs Monitoring	x	x	x	x	x	x	x	x	x	x	x	
Physical/Neuro Exam	x	x	x			x	x	x	x	x	x	x
TSQM	x	x	x			x	x	x	x	x	x	
CIP-PRO20	x	x	x			x	x	x	x	x	x	
R-ODS	x	x	x			x	x	x	x	x	x	
SF-36	x	x	x			x	x	x	x	x	x	
Hand-held Dynamometry	x	x	x			x	x	x	x	x	x	
20-ft Timed Walk	x	x	x			x	x	x	x	x	x	
Electrocardiogram (ECG)	x											
PT/INR, PTT	x											
TSH	x											
Quantitative IgA, IgG, IgM	x	x				x	x	x	x	x	x	
Hematology, blood chemistry	x		x			x	x	x	x	x	x	x
Urine Pregnancy Test	x	x	x			x	x	x	x	x	x	
Subcutaneous Drug Administration Training	x	x	x	x								
Subcutaneous Drug Administration	x	x	x	x								
Drug Diary Training	x	x										
Drug Diary Review				x	x	x	x	x	x	x	x	
Drug Dispensation	x	x	x	x	x	x	x	x	x	x	x	
Drug Accountability							x	x	x	x	x	

\* optional for additional administration training (can be completed at home)

Specific Aim #3. To test the hypothesis SCIG is associated with better QOL.

At baseline (pretreatment of SCIG, while subjects are being treated with IVIG), QOL and treatment satisfaction questionnaires (SF-36, CIP-PRO20, R-ODS, and TSQM) will be done. These measures will be repeated monthly during the course of the study. Data from pretreatment and treatment with SCIG phase will be compared using appropriate statistical methods with correction for multiple comparisons.

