## R-ODS Questionnaire

Protocol: A Study of Subcutaneous Immunoglobulin as Chronic Treatment for Patients with Chronic Inflammatory Demyelinating Polyneuropathy				R-ODS
Are you able to:	0: Impossible to perform	1: Performed with difficulty	2. Easily Performed	
Read a newspaper/book?				
Eat?				
Brush your teeth?				
Wash upper body?				
Sit on a toilet?				
Make a sandwich?				
Dress your upper body?				
Wash your lower body?				
Move a chair?				
Turn a key in a lock?				
Go to a general practitioner?				
Take a shower?				
Do the dishes?				
Do the shopping?				
Catch an object (e.g. ball)?				
Bend and pick up an object?				
Walk 1 flight of stairs?				
Travel by public transport?				
Walk and avoid obstacles?				
Walk outdoors < 1km?				
Carry and put down a heavy object?				
Dance?				
Stand for hours?				
Run?				
				Total Score: _____
Completed by: _____				Date: _____

## APPENDIX 7

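### The CIP-PRO20 form in Appendix 3 is printed under a stem that does not fit its statements and allows a reversed reading; its score range and direction are not stated.

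*Combined protocol and SAP*

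**What the plan says.** Under Specific Aim #3, pretreatment "QOL and treatment satisfaction questionnaires (SF-36, CIP-PRO20, R-ODS, and TSQM) will be done", and these measures are repeated monthly and compared with the SCIG treatment phase. The sample size and statistical analysis paragraph plans a Wilcoxon paired test on each patient's before-to-after change, at the 0.05 level.

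The text for Specific Aim #1 in the Design section names the "CIP-PRO20 scale (used by permission from" its holder and refers to Appendix 3. There the form prints "Are you able to" above 15 first-person statements. Examples are "I have trouble getting dressed because of my neuropathy" and "I am unable to do all the leisure activities that I want to do because of my neuropathy"; the last is "I have trouble doing activities around the house". The answers are 0 for not at all, 1 for a little bit and 2 for a lot, followed by one total score.

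The R-ODS form in Appendix 6 has the same stem above activities. Its answers start at "0: Impossible to perform" and end at 2 for easily performed.

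The abbreviation list expands CIP-PRO20 as "Chronic Immune-mediated Polyneuropathy – Patient Reported Outcome Scale". Neither that list nor any other section gives the number of items, the score range or the scoring direction.

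**The concern.** The stem asks about ability, while the statements describe problems. Answering 2 to the stem is a good result; answering 2 to the statement is a bad one. The leisure item shows the clash most sharply, because it states an inability under a question about ability.

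Patients meet this form alongside a similar one on which the same stem is correct and the scoring runs the other way. With no stated direction or range, site staff have nothing in the protocol against which to notice a reversed form. Double data entry, as planned under Data Management, catches transcription errors but not an answer given in the wrong sense, and the total alone does not reveal one.

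Each patient is his or her own control, so a reading that changes between visits appears as a change in quality of life when health has not changed.

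**Working it through.** **Inputs.** Items printed in Appendix 3: 15 (counted). Score per item: 0 to 2. Items printed in Appendix 6: 24 (counted). Visits: the CIP-PRO20 and R-ODS rows of Table 2 are both marked at screening, Day 1, and Weeks 1, 4, 8, 12, 16, 20 and 24, which is nine visits. The plan states no range or direction to reproduce.

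**Range as printed.** CIP-PRO20: 15 × 2 = 30, so 0 to 30. R-ODS: 24 × 2 = 48, so 0 to 48. If the 20 in the name were an item count (an assumption), the CIP-PRO20 range would be 0 to 20 × 2 = 40.

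**Direction.** All 15 statements describe a problem, so more is worse on every one; none runs the other way. Answered as written, the total is consistent, with higher worse.

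**Shift from a reversed reading at one visit.** An item with true score s is recorded as 2 − s. For k reversed items the total moves by the sum of (2 − 2s), which is at most 2k in either direction.

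- Five items worded as having trouble with something (dressing, sleeping, driving, eating, activities around the house): at most 2 × 5 = 10 points, and 10/30 = 33% of the range.
- Adding work and leisure, k = 7: at most 2 × 7 = 14 points, and 14/30 = 47%.
- An item with true score 1 does not move (2 − 1 = 1), so the maximum needs every reversed item at 0 or at 2.

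Which items a patient would read against the stem is a judgement; five and seven are two reasonable counts.

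**Same reversed reading at every visit.** Let each item truly improve by one point. The recorded change is −(15 − k) + k = 2k − 15.

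- k = 5: −5, still an improvement.
- k = 7: −1, still an improvement.
- k = 8: +1, the sign turns.

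Under uniform change, a constant misreading of the activity items weakens the effect but does not reverse it.

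**Effect on the paired test, extreme case.** Suppose every correctly read patient improves, there are no ties, and the misreaders have the largest shifts, in the wrong direction. The exact two-sided signed-rank p-values are:

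| Patients | Source of the number | No misreader | With misreaders |
|---|---|---|---|
| 8 | interim analysis | 0.008 | one: 0.195 |
| 15 | 22.5 months ÷ 1.5 months per patient | 0.0001 | two: 0.083 |
| 30 | enrolment maximum | below 0.0001 | four: 0.014; five: 0.058 |

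This shows how sensitive the test could be. It says nothing about how often misreading would occur.

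**The case against.** The strongest reply is that patients will answer the statements. They are complete sentences, they all run one way, and the answer options fit them. The stem forms no sentence with any row. The Data Management section also has the data collected by study staff described as proficient in these methods, although the safety monitoring section has subjects completing the instruments. This stands against any claim that misreading is demonstrated. It does not remove the opening for it, because the activity rows invite an ability answer and the R-ODS form trains patients in that answer.

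A reader might infer that the total cannot be interpreted at all. The documents do not support that: answered as written, it is a 0 to 30 score with higher worse.

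A reader might also infer that five items are missing. In favour, the SF-36 is defined as a 36-item form and prints 36 items. But no section says that 20 is an item count, and rows could have been lost when the file was converted to text, although the table shows no visible break. A shorter form, used unchanged throughout, would affect the range and comparability with other uses of the scale. It would not bias the comparison before and after treatment.

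Finally, this is one of four Aim 3 questionnaires in an open-label pilot, and the primary efficacy endpoint is dynamometry at Week 24. That limits the weight of the point.

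**Conclusion.** The point holds as a form error with a cheap remedy. The stem does not match the statements, the same stem is used correctly on a companion form with the opposite scoring direction, and the protocol does not state the CIP-PRO20 range or direction. That the stem was carried over from the R-ODS form is a reasonable inference, not a stated fact.

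The size is at most 10 of 30 points for one patient at one visit, assuming five reversed items all at an extreme, or 14 of 30 with seven. The expected effect is unknown, because the documents give no rate of misreading. A reader might infer that a patient who follows the stem throughout would have improvement recorded as worsening. Under uniform change that needs at least 8 of the 15 items reversed, more than the activity items supply.

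The item count is a separate, unresolved question and has no bearing on direction.

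**What to change.** Before the form is used:

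1. Replace the stem with the wording of the permitted version of the scale, or remove it so that patients rate how much each statement applies to them.
2. State in Specific Aim #3 the CIP-PRO20 score range and that a higher total is worse, after confirming both against the permitted version.
3. Separately, check the 15 printed items against that version. Either add what is missing, or record that the 15-item form is the intended one.

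If forms have already been completed on the present print, keep each patient's baseline and follow-up on one form version, so that the pairs needed by the Wilcoxon test stay intact. Then report a sensitivity analysis by form version. Splitting one patient's forms between versions would itself break the comparison.

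The cost is one reprinted page, a sentence in Aim 3 and, if versions are mixed across patients, a small additional analysis. No visit or measurement is added.

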## TSQM

**TSQM** *(Version II)***Treatment Satisfaction Questionnaire for Medication**

---

**Instructions: Please take some time to think about your level of satisfaction or dissatisfaction with the medication you are taking in this clinical trial. We are interested in your evaluation of the effectiveness, side effects, and convenience of the medication *over the last two to three weeks, or since you last used it*. For each question, please place a single check mark next to the response that most closely corresponds to your own experiences.**

1. How satisfied or dissatisfied are you with the ability of the medication to prevent or treat the condition?

- 1 Extremely Dissatisfied
- 2 Very Dissatisfied
- 3 Dissatisfied
- 4 Somewhat Satisfied
- 5 Satisfied
- 6 Very Satisfied
- 7 Extremely Satisfied

2. How satisfied or dissatisfied are you with the way the medication relieves symptoms?

- 1 Extremely Dissatisfied
- 2 Very Dissatisfied
- 3 Dissatisfied
- 4 Somewhat Satisfied
- 5 Satisfied
- 6 Very Satisfied
- 7 Extremely Satisfied

3. As a result of taking this medication, do you experience any side effects at all?

- 1 Yes
- 0 No

4. How dissatisfied are you by side effects that interfere with your physical health and ability to function (e.g., strength, energy levels)?

- 1 Extremely Dissatisfied
- 2 Very Dissatisfied

- 3 Somewhat Dissatisfied
- 4 Slightly Dissatisfied
- 5 Not at all Dissatisfied
- (5) Not Applicable

5. How dissatisfied are you by side effects that interfere with your mental function (e.g., ability to think clearly, stay awake)?

- 1 Extremely Dissatisfied
- 2 Very Dissatisfied
- 3 Somewhat Dissatisfied
- 4 Slightly Dissatisfied
- 5 Not at all Dissatisfied
- (5) Not Applicable

6. How dissatisfied are you by side effects that interfere with your mood or emotions (e.g., anxiety/fear, sadness, irritation/anger)?

- 1 Extremely Dissatisfied
- 2 Very Dissatisfied
- 3 Somewhat Dissatisfied
- 4 Slightly Dissatisfied
- 5 Not at all Dissatisfied
- (5) Not Applicable

7. How satisfied or dissatisfied are you with how easy the medication is to use?

- 1 Extremely Dissatisfied
- 2 Very Dissatisfied
- 3 Dissatisfied
- 4 Somewhat Satisfied
- 5 Satisfied
- 6 Very Satisfied
- 7 Extremely Satisfied

8. How satisfied or dissatisfied are you with how easy it is to plan when you will use the medication each time?

- 1 Extremely Dissatisfied
- 2 Very Dissatisfied
- 3 Dissatisfied
- 4 Somewhat Satisfied
- 5 Satisfied
- 6 Very Satisfied
- 7 Extremely Satisfied

9. How satisfied or dissatisfied are you by how often you are expected to use/take the medication?

- 1 Extremely Dissatisfied
- 2 Very Dissatisfied
- 3 Dissatisfied
- 4 Somewhat Satisfied
- 5 Satisfied
- 6 Very Satisfied
- 7 Extremely Satisfied

10. How satisfied are you that the good things about this medication outweigh the bad things?

- 1 Extremely Dissatisfied
- 2 Very Dissatisfied
- 3 Dissatisfied
- 4 Somewhat Satisfied
- 5 Satisfied
- 6 Very Satisfied
- 7 Extremely Satisfied

11. Taking all things into account, how satisfied or dissatisfied are you with this medication?

- 1 Extremely Dissatisfied
- 2 Very Dissatisfied
- 3 Dissatisfied
- 4 Somewhat Satisfied
- 5 Satisfied
- 6 Very Satisfied
- 7 Extremely Satisfied

**APPENDIX 5**  
**HAND HELD DYNAMOMETRY WORKSHEET**

Protocol: A Study of Subcutaneous Immunoglobulin as Chronic Treatment for Patients with Chronic Inflammatory Demyelinating Polyneuropathy							HHD
Not Tested	Muscle	Trial 1 (lbs.)	Trial 2 (lbs.)	Trial 3 (lbs.) if needed	Able to break?		If not tested, please explain:
					Yes	No	
	Left shoulder flexion						 Subject unable to perform task due to weakness  Other (specify _____)
	Right shoulder flexion						 Subject unable to perform task due to weakness  Other (specify _____)
	Left elbow flexion						 Subject unable to perform task due to weakness  Other (specify _____)
	Right elbow flexion						 Subject unable to perform task due to weakness  Other (specify _____)
	Left elbow extension						 Subject unable to perform task due to weakness  Other (specify _____)
	Right elbow extension						 Subject unable to perform task due to weakness  Other (specify _____)
	Left wrist extension						 Subject unable to perform task due to weakness  Other (specify _____)
	Right wrist extension						 Subject unable to perform task due to weakness  Other (specify _____)
	Left hip flexion						 Subject unable to perform task due to weakness  Other (specify _____)
	Right hip flexion						 Subject unable to perform task due to weakness  Other (specify _____)
	Left knee extension						 Subject unable to perform task due to weakness  Other (specify _____)
	Right knee extension						 Subject unable to perform task due to weakness  Other (specify _____)
	Left knee flexion						 Subject unable to perform task due to weakness  Other (specify _____)
	Right knee flexion						 Subject unable to perform task due to weakness  Other (specify _____)
	Left ankle dorsiflexion						 Subject unable to perform task due to weakness  Other (specify _____)
	Right ankle dorsiflexion						 Subject unable to perform task due to weakness  Other (specify _____)
	Left first dorsal interosseous						 Subject unable to perform task due to weakness  Other (specify _____)
	Right first dorsal interosseous						 Subject unable to perform task due to weakness  Other (specify _____)
Completed by: _____							Date: _____

## APPENDIX 6

## R-ODS Questionnaire

Protocol: A Study of Subcutaneous Immunoglobulin as Chronic Treatment for Patients with Chronic Inflammatory Demyelinating Polyneuropathy				R-ODS
Are you able to:	0: Impossible to perform	1: Performed with difficulty	2. Easily Performed	
Read a newspaper/book?				
Eat?				
Brush your teeth?				
Wash upper body?				
Sit on a toilet?				
Make a sandwich?				
Dress your upper body?				
Wash your lower body?				
Move a chair?				
Turn a key in a lock?				
Go to a general practitioner?				
Take a shower?				
Do the dishes?				
Do the shopping?				
Catch an object (e.g. ball)?				
Bend and pick up an object?				
Walk 1 flight of stairs?				
Travel by public transport?				
Walk and avoid obstacles?				
Walk outdoors < 1km?				
Carry and put down a heavy object?				
Dance?				
Stand for hours?				
Run?				
				Total Score: _____
Completed by: _____				Date: _____

## APPENDIX 7

## Short Form-36 Questionnaire

Protocol: A Study of Subcutaneous Immunoglobulin as Chronic Treatment for Patients with Chronic Inflammatory Demyelinating Polyneuropathy	SF-36
--	--------------

1. In general, would you say your health is:	 1 - Excellent  2 - Very good  3 - Good  4 - Fair  5 - Poor
2. Compared to one year ago, how would you rate your health in general now?	 1 - Much better than one year ago  2 - Somewhat better than one year ago  3 - About the same as one year ago  4 - Somewhat worse now than one year ago  5 - Much worse now than one year ago

The following questions are about activities you might do during a typical day. Does your health now limit you in these activities? If so, how much?	Response: 1 - Yes, limited a lot 2 - Yes, limited a little 3 - No, not limited at all		
3. Vigorous activities , such as running, lifting heavy objects, participating in strenuous sports.	 1	 2	 3
4. Moderate activities , such as moving a table, pushing a vacuum cleaner, bowling or playing golf	 1	 2	 3
5. Lifting or carrying groceries	 1	 2	 3
6. Climbing several flights of stairs	 1	 2	 3
7. Climbing one flight of stairs	 1	 2	 3
8. Bending, kneeling or stooping	 1	 2	 3
9. Walking more than a mile	 1	 2	 3
10. Walking several blocks	 1	 2	 3
11. Walking one block	 1	 2	 3
12. Bathing or dressing yourself	 1	 2	 3

	Response:
--	-----------

During the past 4 weeks, have you had any of the following problems with your work or other regular daily activities as a result of your physical health?	1 - Yes	2 - No
13. Cut down on the amount of time you spent on work or other activities	 1	 2
14. Accomplished less than you would like	 1	 2
15. Were limited in the kind of work or other activities	 1	 2
16. had difficulty performing the work or other activities (took extra effort)	 1	 2

During the past 4 weeks, have you had any of the following problems with your work or other regular daily activities as a result of any emotional problems (such as feeling depressed or anxious)?	Response: 1 - Yes 2 - No	
17. Cut down the amount of time you spent on work or other activities	 1	 2
18. Accomplished less than you would like	 1	 2
19. Didn't do work or other activities as carefully as usual	 1	 2

20. During the past 4 weeks, to what extent has your physical health or emotional problems interfered with your normal social activities with family, friends, neighbors or groups?	 1 - Not at all  2 - Slightly  3 - Moderately  4 - Quite a bit  5 - Extremely
21. How much bodily pain have you had during the past 4 weeks?	 1 - None  2 - Very Mild  3 - Mild  4 - Moderate

		 5 - Severe  6 - Very severe
22. During the past 4 weeks, how much did pain interfere with your normal work (including both work outside the home and housework)?		 1 - Not at all  2 - A little bit  3 - Moderately  4 - Quite a bit  5 - Extremely

These questions are about how you feel and how things have been with you during the past 4 weeks. For each question, please give the one answer than comes closest to the way you have been feeling, how much of the time during the past 4 weeks
		
Response:
 
1 - All of the time 2 - Most of the time 3 - A good bit of the time 4 - Some of the time 5 - A little of the time 6 -None of the time

23. Did you feel full of pep?		 1  2  3  4  5  6
24. Have you been a very nervous person?		 1  2  3  4  5  6
25. Have you felt so down in the dumps that nothing could cheer you up?		 1  2  3  4  5  6
26. Have you felt calm and peaceful?		 1  2  3  4  5  6
27. Did you have a lot of energy?		 1  2  3  4  5  6
28. Have you felt downhearted and blue?		 1  2  3  4  5  6
29. Did you feel worn out?		 1  2  3  4  5  6
30. Have you been a happy person?		 1  2  3  4  5  6
31. Did you feel tired?		 1  2  3  4  5  6

32. During the past 4 weeks, how much of the time has your physical health or emotional problems interfered with your social activities (like visiting friends, relatives, etc.)?	 1 - All of the time  2 - Most of the time  3 - Some of the time  4 - A little of the time  5 - None of the time
---	--

How TRUE or FALSE is each of the following statements for you?	Response: 1 - Definitely true 2 - Mostly true 3 - Don't know 4 - Mostly false 5 - Definitely false				
33. I seem to get sick a little easier than other people	 1	 2	 3	 4	 5
34. I am as healthy as anybody I know	 1	 2	 3	 4	 5
35. I expect my health to get worse	 1	 2	 3	 4	 5
36. My health is excellent.	 1	 2	 3	 4	 5

Total Score: \_\_\_\_\_

Completed by: \_\_\_\_\_ Date: \_\_\_\_\_
